6.1.1. Overview of TEAEs

An overview of TEAEs reported through the study will be provided. The overview will include summaries of subjects with TEAEs, with TEAEs related to siltuximab treatment, with TEAEs of maximum toxicity grade of 1 to 5, SAEs, TEAEs leading to discontinuation of siltuximab treatment.

To account for the different siltuximab exposure times, an exposure-adjusted incidence rates (EAIR) analysis will be performed in the overview of TEAEs summary and for selected TEAEs. More specifically, the incidence rates will be normalized by the exposure time, which is defined as month from first dose date of siltuximab treatment to first onset date of the corresponding TEAE for those who experienced the event and the entire treatment duration for those who never experienced such a TEAE. All reported EAIR is the incidence rate per 100 patient-months at risk.

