4.3. Extent of Exposure

Long-term treatment with siltuximab will be summarized and presented based on the safety population by combining parent study and extension study.

Duration of study treatment, defined as the number of years from the date of the first administration of siltuximab treatment to the date of the last administration of siltuximab treatment, will be summarized by descriptive statistics. In addition, the number and percentage of subjects who were on siltuximab treatment for more than 1, 2, 3, 4, 5, 6, 7 and 8 years will be provided.

The total number of siltuximab administrations including cumulative dose (mg/kg) administered across both parent and extension studies will be summarized.

The number of subjects with siltuximab dose delays including reasons (AE or other) for dose delays in the long-term safety extension study of CNT0328MCD2002 will be reported.

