6.1. Adverse Events

All adverse events, regardless of seriousness, severity, or presumed relationship to study therapy, will be recorded in standard medical terminology. All toxicities will be graded according to graded according to the National Cancer Institute Common Terminology Criteria for Adverse Events (NCI-CTCAE), Version 4.0. For AE reporting, the verbatim term used in the CRF by investigators to identify adverse events will be coded to a system organ class (SOC) and a preferred term (PT) using the latest version of Medical Dictionary for Regulatory Activities (MedDRA) coding dictionary.

Unless otherwise specified, at each level (e.g., system organ class and/or preferred term) of subject summarization in reporting the incidence of the AE, a subject is counted once if one or more events were recorded.

All summaries of AEs will be based on treatment-emergent adverse events (TEAEs). TEAEs are defined as any AE that occurs after start of the first siltuximab through 30 days after the last study siltuximab treatment; or the day prior to start of subsequent anticancer therapy, whichever is earlier; or any AE that is considered drug-related (very likely, probably, or possibly related) regardless of the start date of the event; or any AE that is present at baseline but worsens in toxicity grade or is subsequently considered drug-related by the investigator.

The incidence of TEAEs will be summarized overall, by MedDRA system organ class (SOC) and preferred term, by toxicity grade, by relationship to siltuximab treatment, and by number of years of siltuximab exposure. Specifically, the following AE summaries will be presented:

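### The TEAE overview applies exposure-adjusted rates to maximum-grade rows, which biases the Grade 1 to 4 rates downward, and more so the longer the exposure

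*SAP*

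**What the plan says.** SAP 6.1.1 (Overview of TEAEs) builds a summary whose rows include subjects "with TEAEs of maximum toxicity grade of 1 to 5", next to rows for any TEAE, related TEAEs, SAEs and TEAEs leading to discontinuation. It then says that an EAIR "analysis will be performed in the overview of TEAEs summary and for selected TEAEs", with the aim given as "To account for the different siltuximab exposure times".

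Time at risk starts at the first siltuximab dose. It ends at the "first onset date of the corresponding TEAE for those who experienced the event", and is "the entire treatment duration for those who never experienced such a TEAE". On the unit, the SAP says: "All reported EAIR is the incidence rate per 100 patient-months at risk". No separate rule is given for the maximum-grade rows.

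Exposure is expected to differ widely. SAP 4.3 combines parent and extension treatment and counts subjects "on siltuximab treatment for more than 1, 2, 3, 4, 5, 6, 7 and 8 years".

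SAP 6.1.3 plans another exposure-adjusted analysis, for selected TEAEs of Grade 3 or above. That is a cumulative threshold, not a maximum-grade class.

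**The concern.** An incidence rate for first onset needs an event whose occurrence is settled when it happens. Maximum grade is settled only at the end of follow-up, and the classes exclude one another. A Grade 2 event counts in the maximum-Grade-2 row only if the subject never has anything worse. Once a worse event is on record, earlier or later, the Grade 2 event leaves the numerator and the subject's whole treatment time enters the denominator.

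Longer-treated subjects have more time to acquire a worse event, so the understatement grows with exposure. That is the opposite of what the EAIR is for. Long-term safety is the primary objective, and a reader of the overview would take these figures as rates of low- and mid-grade toxicity per unit of exposure.

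**Working it through.** **Inputs.** The rows, the time-at-risk rule and the unit come from SAP 6.1.1. The follow-up range of 12 to 96 months reflects the exposure bands in SAP 4.3. The documents state no EAIR and no event rate, so there is no figure of the plan's own to reproduce, and every onset rate below is an assumption.

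**Step 1: one subject.** Grade 2 TEAE at month 3, Grade 3 TEAE at month 50, treated for 72 months. With data to month 24, this subject gives the maximum-Grade-2 row 1 event and 3 months. With data to month 72, the same subject gives it 0 events and 72 months. The Grade 2 event itself has not changed.

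**Step 2: direction.** Compare the maximum-grade row with a row for any event of the same grade, having n events in D patient-months. Each subject with a worse event takes 1 from n and adds (treatment time − onset time) to D. That addition is not negative when onset falls within treatment. If onset falls d months after the last dose, the rate still drops provided d < D/n. At 10 per 100 patient-months D/n is 10 months, while the post-treatment TEAE window is 30 days. The downward direction therefore does not depend on how the hazard behaves over time.

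**Step 3: formula under constant risk.** Let L be the monthly onset rate for the grade, H the summed rate of all worse grades, T the follow-up, S = exp(−HT) and p = 1 − exp(−LT).
- Expected events per subject: S·p
- Expected time at risk: S·p/L + (1 − S)·T
- EAIR = 1 / [1/L + (1 − S)·T/(S·p)]

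This falls strictly with T whenever H > 0, and equals L for Grade 5, where H = 0.

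Example, Grade 2 at 10 per 100 patient-months with worse grades at 2 + 0.4 + 0.1 = 2.5:
- T = 12: S = exp(−0.30) = 0.741, p = 0.699; EAIR = 1/(10 + 3.110/0.518) = 0.0625, or 6.25 per 100 patient-months.
- T = 72: S = exp(−1.80) = 0.165, p = 0.999; EAIR = 1/(10 + 60.10/0.165) = 0.0027, or 0.27.

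**Step 4: simulation.** 300,000 subjects per setting, independent onset times, with a Grade 5 event ending exposure. Assumed onset rates for Grades 1/2/3/4/5, per 100 patient-months: low 5/3/0.8/0.15/0.05; mid 20/10/2/0.4/0.1; high 40/25/4/0.8/0.2. Maximum-grade EAIR at 12 → 72 months:

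| Row | Low | Mid | High |
|---|---|---|---|
| Max Grade 1 | 2.74 → 0.08 | 1.97 → <0.001 | 0.24 → <0.001 |
| Max Grade 2 | 2.62 → 0.86 | 6.32 → 0.28 | 7.08 → 0.04 |
| Max Grade 3 | 0.785 → 0.680 | 1.88 → 1.16 | 3.49 → 1.05 |
| Max Grade 4 | 0.149 → 0.148 | 0.397 → 0.385 | 0.795 → 0.729 |
| Grade 5 | flat | flat | flat |

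Relative falls (low, mid, high): Grade 2 67%, 96%, 99%; Grade 3 13%, 38%, 70%; Grade 4 about 1%, 3%, 8%. The Step 3 formula, in which death does not shorten exposure, gives somewhat larger Grade 4 falls (low 0.149 → 0.144, or 3%; high 0.780 → 0.665, or 15%).

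**Step 5: departures from constant risk.**
- Rising hazard (Weibull shape 1.5, mid scale): the Grade 3 row rises from 0.95 at 12 months to 1.58 at 60, then falls to 1.31 at 96. The Grade 4 row rises from 0.09 to 0.235. The Grade 3 row stays below the any-Grade-3 rate, and by more as time passes: 0.95 against 0.96 at 12 months, 1.58 against 1.92 at 60, 1.31 against 2.13 at 96.
- Subject-level frailty, mid rates: the any-Grade-2 rate itself falls from 6.87 to 4.18 between 12 and 72 months. The maximum-Grade-2 row falls from 3.98 to 0.46.

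**Step 6: threshold rows.** With time to first event at or above each grade, the mid-scenario EAIRs for ≥1, ≥2, ≥3, ≥4 and 5 are about 32.5, 12.5, 2.5, 0.50 and 0.10 at every follow-up from 12 to 96 months. These are the sums of the assumed rates.

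**The case against.** The SAP does not say row by row that each maximum-grade line carries an EAIR, and it leaves details of derived variables to a data presentation specification that is not among the documents. The wording for subjects without the event could be stretched so that someone with a recorded Grade 2 event is not treated as event-free. These points stand as limits: the application is the natural reading, not an explicit statement. But no row is exempted and neither alternative is written down. Under the stretched reading, the rate would no longer match its row label.

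The clinically weightier figures are also largely protected. SAP 6.1.3 already uses a Grade 3 or higher threshold for selected TEAEs, and the any-TEAE, related, SAE and discontinuation rows do not have the defect. Showing maximum grade as counts and percentages is a normal display. All of this stands, and it narrows the problem to the overview EAIRs, mainly for Grades 1 and 2.

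Two stronger readings are tempting. A reader might infer that all four rates must fall with follow-up whatever the underlying risk. They need not: with rising hazards the Grade 3 and 4 rows can rise, and with heterogeneous subjects part of any fall has another cause. A reader might also infer that 2-year and 6-year EAIRs will be set against each other and show toxicity fading. The documents do not support that: SAP section 3 does not mention the EAIR for the interim analysis, no such comparison is planned, and the planned display by years of treatment is TEAE incidence.

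**Conclusion.** As written, the EAIR is wrong for the maximum Grade 1 to 4 rows of the overview. It understates the onset rate for the grade, increasingly so with longer exposure, which defeats its stated purpose. The direction follows from the counting rule. The size depends on assumed rates, on independence between grades and, for the quoted falls, on constant risk: severe for Grades 1 and 2, moderate to large for Grade 3, small for Grade 4, none for Grade 5. The conclusion rests on reading SAP 6.1.1 as applying the EAIR to every overview row.

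**What to change.** In SAP 6.1.1, state that the maximum-grade rows are reported as n (%) only. For the EAIR part of the overview, add rows for any TEAE of Grade ≥2, ≥3, ≥4 and 5; Grade ≥1 is the existing any-TEAE row. Time at risk for each row runs from first siltuximab to the first onset of a TEAE at or above that grade, or is the full treatment duration if there is none. This matches the form that SAP 6.1.3 already uses.

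The cost is one SAP sentence and a change to the table shell. No new data are needed. The reported low-grade rates will look less favourable.

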## 4 STUDY POPULATION

### 4.1 General Considerations

The inclusion and exclusion criteria for enrolling subjects in this study are described in the following sections. No deviations from these criteria are allowed. **NOTE:** Investigators must ensure that all inclusion and exclusion criteria have been met at screening. Re-screening of screening failures is allowed. A subject is considered eligible if the last observation prior to the first dose meets the inclusion and exclusion criteria.

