### 4.3 Exclusion Criteria

Potential subjects who meet any of the following criteria will be excluded from participating in the study:

1. Unmanageable toxicity, an adverse event, progression of disease, or withdrawal of consent as reason for discontinuing treatment from previous sponsor-initiated siltuximab study.
2. Vaccination with live, attenuated vaccines within 4 weeks of first dose of this study.
3. Criterion removed per amendment INT-2 (see protocol amendment table before Synopsis).
4. Known unmanageable allergies, hypersensitivity, or intolerance to monoclonal antibodies or to murine, chimeric, or human proteins or their excipients.

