2.4. Siltuximab Treatment Date

Siltuximab treatment date is the date on which a subject actually received siltuximab (partial or complete) administration.

For subjects who previously received siltuximab treatment, the first siltuximab treatment date is defined as the earliest date of non-zero dose of siltuximab administration from study C0328T03 or CNTO328MCD2001. The last study treatment date is defined as the latest date of non-zero dose of siltuximab administration from CNTO328MCD2002.

For subjects who were siltuximab-naive, the first study treatment date is defined as the earliest date of non-zero dose of siltuximab from study CNTO328MCD2002. The last study treatment date is defined as the latest date of non-zero dose of siltuximab administration from study CNTO328MCD2002.

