4. SUBJECT INFORMATION

4.1. Demographics and Baseline Characteristics

Because demographics and baseline disease characteristics were not collected in the current long-term safety extension study of CNTO328MCD2002, therefore, demographics and baseline characteristics variables will be summarized based on data collected in the parent study of C0328T03 or CNTO328MCD2001.

Subject demographic and baseline characteristic variables: age (<65 years; ≥65 years), sex, race, weight (kg), height (cm) and ECOG performance score will be summarized.

Baseline disease characteristics including Castleman's disease histology (hyaline vascular; plasmacytic, mixed, undetermined) based on local pathology review, type of disease (unicentric, multicentric), HHV-8 status (positive, negative), and years since disease diagnosis (years) will be tabulated.

The distribution of subject enrollment to the long-term safety extension will be presented according to region and country. Subjects who did not meet inclusion/exclusion criteria for long-term extension study will be listed by subject ID and specific criteria not met.

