6.1.7. TEAEs Leading to Discontinuation of Siltuximab Treatment

A summary of number of subjects who discontinued siltuximab treatment because of 1 or more TEAEs by MedDRA system-organ class and preferred term will be provided. The summaries will be presented by all Grades and Grade 3 or higher. This table includes associated TEAEs for those subjects who discontinued siltuximab treatment due to an adverse event reported on the “End of Treatment” CRF page.

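### If the overview EAIR covers TEAEs leading to discontinuation and Grade 5 TEAEs, parent-study months bias both rates downward; separately, the drug-related TEAE clause has no lower date bound

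*SAP*

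**What the plan says.** **Rates.** SAP 6.1.1 states that "an exposure-adjusted incidence rates (EAIR) analysis will be performed in the overview of TEAEs summary and for selected TEAEs". The overview it describes includes maximum toxicity grade 1 to 5 and TEAEs leading to discontinuation. It does not say which rows receive a rate. A subject with the event contributes "exposure time, which is defined as month from first dose date of siltuximab treatment to first onset date of the corresponding TEAE"; a subject without it contributes the whole treatment duration. Rates are per 100 patient-months at risk.

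**Clock.** For previously treated subjects, SAP 2.4 says "the first siltuximab treatment date is defined as the earliest date of non-zero dose of siltuximab administration from study C0328T03 or CNTO328MCD2001". For siltuximab-naive subjects the date comes from the extension. SAP 2.2 and 4.3 pool AEs and exposure across parent and extension studies. SAP 2.2 describes the analysed subjects as those treated in CNTO328MCD2002.

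**Entry.** Protocol 4.3 excludes a subject with "Unmanageable toxicity, an adverse event, progression of disease, or withdrawal of consent as reason for discontinuing treatment" in a previous sponsor siltuximab study. Protocol 4.1 adds: "No deviations from these criteria are allowed". SAP 4.1 nevertheless provides that "Subjects who did not meet inclusion/exclusion criteria for long-term extension study will be listed by subject ID and specific criteria not met".

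**TEAE definition.** Protocol 11.3 requires onset on or after the first siltuximab dose and no later than 30 days after the last, within the 6-year cutoff. SAP 6.1 uses a similar window in its first clause. It then adds any AE judged possibly, probably or very likely related, whatever its start date.

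**The concern.** Subjects are analysed because they reached the extension. To do so, a previously treated subject had to be alive and not to have stopped parent treatment for an AE. For those two outcomes the parent months are therefore guaranteed event-free, yet they count as months at risk, and no delayed entry is planned. Long-term safety is the primary objective and the EAIR is the SAP's tool for unequal exposure. A rate for AE-related stopping or fatal AEs that errs only in the favourable direction would mislead a reader.

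The second issue is separate. A TEAE clause with no lower date bound, applied to AE data that begin at parent-study start, can reach back before any siltuximab was given. The TEAE flag feeds every AE summary.

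**Working it through.** The documents state no EAIR, expected event count or expected extension exposure, so there is no planned figure to reproduce. The direction follows from the text; the size can only be illustrated.

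**Part 1: inputs**
- P, parent siltuximab months: protocol 1.1.2.1 gives a median of 331 days for C0328T03, an early report of one parent study. 331/30.4375 = 10.87 months. It is used here as a mean (assumption). Exposure in CNTO328MCD2001 is not given.
- f, siltuximab-naive share: protocol 1.1.2.2 randomises about 78 subjects 1:2, so about 78/3 = 26 receive placebo. If all 26 enter naive among 75, f = 26/75 = 0.347. Protocol 3.1 expects a majority on active siltuximab, so f is below 0.5.
- E, mean extension months at risk: not given. The 6-year cutoff caps it at about 72. Assumed values: 24, 48 and 72.

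**Formula.** Every countable stop or death falls in the extension, apart from an eligibility violation. The event count cancels:

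planned rate / extension-only rate = E / (E + (1 − f)P)

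For E = 48 and f = 0: 48/(48 + 10.87) = 0.815, so 18.5% lower.

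| E (months) | f = 0 | f = 0.347 | f = 0.5 |
|---|---|---|---|
| 24 | 31.2% lower | 22.8% | 18.5% |
| 48 | 18.5% | 12.9% | 10.2% |
| 72 | 13.1% | 9.0% | 7.0% |

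**Against sampling error.** Assume 6 AE discontinuations in 75 subjects with E = 48.
- Extension-only: 100 × 6/(75 × 48) = 100 × 6/3600 = 0.167 per 100 patient-months; exact Poisson 95% interval 0.061 to 0.363.
- Planned, none naive: 100 × 6/4415.6 = 0.136.
- Planned, 26 naive: 100 × 6/(3600 + 49 × 10.87) = 100 × 6/4132.9 = 0.145.

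**AEs that began in the parent study.** The SAP clock ends at AE onset, so an AE that began in the parent study and led to a later stop is counted in parent time. If such an AE begins midway through the parent period, it removes 48 + 5.44 = 53.44 months from the denominator.
- None naive: one such event gives 100 × 6/4362.2 = 0.1375 (17.5% lower); two give 0.1393 (16.4%).
- 26 naive: 0.1471 (11.8%) and 0.1490 (10.6%).

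The dilution shrinks only slightly.

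**Long exposures.** SAP 4.3 will count subjects "on siltuximab treatment for more than 1, 2, 3, 4, 5, 6, 7 and 8 years". With at most about 72 extension months, anyone beyond 8 years has more than 96 − 72 = 24 months before the extension, over 24/96 = 25% of the clock. The number of such subjects is not stated.

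**Part 2: the texts side by side.** Protocol 11.3 sets a lower bound at first siltuximab. The drug-related clause in SAP 6.1 sets none. SAP 2.2 takes AE data from the start of the parent study, and CNTO328MCD2001 was double-blind with a placebo arm whose subjects may enter (protocol 4.2). A placebo-phase AE rated possibly related therefore meets the SAP's words. Under SAP 6.1.1 its time from first siltuximab to onset is negative.

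Illustration (assumed numbers): 20 naive subjects followed for 24 months each, with one such AE 3 months before first siltuximab. Patient-months = 19 × 24 − 3 = 453, and the rate is 100 × 1/453 = 0.22. Under protocol 11.3 there are 0 events in 480 months.

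**The case against.** **On the rates.** The SAP never says that these two rows get an EAIR. SAP 6.1.2 and 6.1.3 plan exposure adjustment only for selected TEAEs. The sections on discontinuation (6.1.7) and deaths (6.2) plan none. A rate for each maximum grade is not an obvious output. Pooling parent and extension data is deliberate and disclosed. No test or threshold uses the rates. Crude counts and listings are planned: SAP 6.1.7 tabulates "those subjects who discontinued siltuximab treatment due to an adverse event reported on the" end-of-treatment form, 4.2 lists discontinuations with reasons, and 6.2 tabulates deaths and lists fatal TEAEs. All of this stands, and it makes the bias conditional and limits the harm to a misleading rate. It does not repair the clock if the rates are produced.

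A reader might infer that the whole overview is diluted. It is not in this way: other rows count parent-period events as well as parent months, although all rows describe subjects selected for having tolerated parent treatment. A reader might also take a much larger size by giving every subject the longest C0328T03 exposure, 1148 days (37.7 months). With E = 24 and nobody naive, that yields 61% lower. It uses one subject's maximum as the average, so it does not support an estimate.

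**On the TEAE clause.** It was probably meant for late related events. The next clause, which covers AEs present at baseline and later judged related, would be largely redundant if any date were already allowed. SAP 2.5 places derived-variable rules in a data presentation specification that is not available here, and a bound may be set there. No placebo-phase related AE is documented. These points make intent doubtful, but the SAP as written still contradicts protocol 11.3.

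It is also tempting to call the end of the SAP window an error, because it cuts at subsequent therapy and admits later related AEs. Protocol 12.2.1 largely explains it: after further MCD therapy within the reporting period only related AEs must be reported, and routine collection ends at 30 days.

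**Conclusion.** Both parts hold as corrections to the SAP's wording.

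Part 1 is conditional. If the EAIR is run on TEAEs leading to discontinuation and on Grade 5 TEAEs, both rates are biased downward. With 10.9 parent months and an assumed 48 extension months the shortfall is roughly 10% to 18%, depending on the naive share. That is smaller than the sampling error for a handful of events, but always in the same direction. Only the direction is documented. The documents do not support saying that the rates will certainly be biased, that any event is hidden, or that the true size is known.

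Part 2 is a contradiction between the SAP's literal clause and protocol 11.3. Whether any AE would be affected cannot be told from the documents. The difference at the end of the window is not a defect and needs at most a note.

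Worth fixing, with medium confidence; no formal conclusion of the study depends on it.

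**What to change.** 1. In SAP 6.1.1, name the overview rows that receive an EAIR. If discontinuation and Grade 5 are among them, start the clock for those two rows at the first CNTO328MCD2002 siltuximab dose, or use delayed entry at that date. Date every event in those rows by one rule, the date of treatment stop or death, whether the AE began in the parent study or the extension. Footnote the time origin. Leave the other rows on the combined clock.
2. In SAP 6.1, limit the drug-related clause to AEs with onset on or after the first siltuximab dose. Optionally note that the end of the window departs from protocol 11.3 and follows the collection rule in 12.2.1.

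Cost: SAP wording, re-derived exposure and event dates for two rows, and a revised TEAE flag. No new data are needed. The two rates will look somewhat less favourable, and the table will carry two time origins, hence the footnote.

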2.6. General Analysis Method

In general, continuous variables will be summarized using descriptive statistics such as mean, standard deviation (SD), median and range. Categorical variables will be summarized using frequency and percentage. For time-to-event variables, the Kaplan-Meier method will be used for descriptive summaries. For the calculation of time-to-event and duration-of-event variables, the difference between the start date and the end date plus 1 day will be used.

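### The exposure-adjusted incidence rate counts events up to 30 days after the last dose, but event-free subjects stop contributing time at the last dose, a small upward bias that one sentence in SAP 6.1.1 would remove

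*SAP*

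**What the plan says.** **Numerator.** SAP 6.1 bases all AE summaries on TEAEs. The main limb of the definition is "any AE that occurs after start of the first siltuximab through 30 days after the last study siltuximab treatment", cut short where needed by "or the day prior to start of subsequent anticancer therapy, whichever is earlier". A further limb has no time limit: "any AE that is considered drug-related (very likely, probably, or possibly related) regardless of the start date of the event". Protocol 11.3 uses the same 30 days and confines them to the 6-year data cutoff.

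**Denominator.** SAP 6.1.1 defines exposure time in two ways:
- With the event: "month from first dose date of siltuximab treatment to first onset date of the corresponding TEAE for those who experienced the event".
- Without the event: "the entire treatment duration for those who never experienced such a TEAE".

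SAP 6.1.1 does not define treatment duration. SAP 4.3 does, for the exposure table: "the number of years from the date of the first administration of siltuximab treatment to the date of the last administration of siltuximab treatment". For time-to-event and duration variables, SAP 2.6 says that "the difference between the start date and the end date plus 1 day will be used", which adds one day and not thirty.

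**Label.** "All reported EAIR is the incidence rate per 100 patient-months at risk". The EAIR is planned for the TEAE overview, for selected TEAEs (SAP 6.1.2) and for selected TEAEs of Grade 3 or higher (SAP 6.1.3).

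**The concern.** A subject is at risk of a countable TEAE until the TEAE window closes. Suppose two subjects stop treatment on the same day. One has a first event 20 days later, and adds one event plus all the time up to that day. The other has no event, and adds nothing after the last dose. Whether post-dose time counts therefore depends on the outcome, which a person-time rate should not allow.

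The omitted time belongs only to event-free subjects, so the denominator can only be too small. The EAIR is the plan's only exposure-normalised rate and was introduced to deal with unequal exposure, yet this error itself varies with exposure: the shorter the treatment, the larger the omitted share. What is at stake is how accurate the reported rates are and whether they match their at-risk label.

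**Working it through.** The documents state no EAIR, expected event rate or exposure total, so there is no planned figure to reproduce. The check asks how far the planned rate departs from the true rate per month at risk.

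**Inputs**
- Post-dose window: 30 days (SAP 6.1). In months, w = 30/30.4375 = 0.986.
- Treatment duration T, first to last dose (SAP 4.3): the values 6, 12, 36 and 60 months are assumed. SAP 4.3 tabulates exposure from more than 1 to more than 8 years.
- Constant event rate L, also applying in the window: 0.2, 1 and 5 per 100 patient-months, assumed.

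**Formula.** Let S = exp(−L(T + w)) be the probability of no event by the end of the window.
- Expected events per subject: 1 − S.
- Expected time at risk per subject: (1 − S)/L.
- Planned time per subject: (1 − S)/L − wS, because each event-free subject loses w.
- Planned rate / true rate = (1 − S) / [(1 − S) − L·w·S].
- For a rare event this tends to (T + w)/T, so the overstatement is w/T.

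**One case in full.** T = 60, L = 0.01: S = exp(−0.6099) = 0.5434. The ratio is 0.4566 / (0.4566 − 0.01 × 0.986 × 0.5434) = 0.4566 / 0.4512 = 1.012.

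**Overstatement with the full 30-day window**

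| T (months) | Rare-event limit | 0.2 per 100 | 1 per 100 | 5 per 100 |
|---|---|---|---|---|
| 60 | 1.6% | 1.5% | 1.2% | 0.2% |
| 36 | 2.7% | 2.6% | 2.3% | 0.9% |
| 12 | 8.2% | 8.1% | 7.7% | 5.7% |
| 6 | 16.4% | 16.3% | 15.8% | 13.4% |

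At the extreme, an event-free subject with a single dose contributes about 1 day instead of up to 31.

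**Pooled cohort, assumed.** Take 75 subjects, 15 treated for 6 months and 60 for 60 months, at a true rate of 1 per 100 patient-months. The planned rate is 1.016, an overstatement of 1.6% (1.9% at a true rate of 0.2 and 1.1% at 5). If the 60 are still on treatment at the cutoff, with an assumed mean of 10.5 days since the last dose, it falls to 0.9%.

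**Check.** Simulation of 400,000 subjects per scenario at 3, 12 and 60 months agreed with the formula within random error. When event-free time ran to the end of the window, the simulated ratios were 0.996 to 1.014, which is 1 within random error.

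**The case against.** **The treatment duration might include the 30 days.** SAP 6.1.1 leaves the term undefined, SAP 4.3 defines it for a different table, and SAP 2.5 sends derived variables to a data presentation specification that is not available here. The final programming could therefore be right. This limits certainty about the derivation, not about the text: no section adds the 30 days, and the only definition given stops at the last dose.

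**The overstatement is conditional.** If no events occurred in the 30 days after the last dose, the planned figure would simply be the on-treatment rate. That stands. So does the point that the tabulated percentages are full-window values. They shrink for subjects still dosing at the cutoff and for those starting subsequent therapy within 30 days.

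**The importance is easy to overstate.** A reader might infer three stronger things that the documents do not support:
- *That the EAIR is the only AE analysis that deals with unequal exposure.* SAP 6.1 and 6.1.2 also tabulate TEAEs by years of siltuximab exposure.
- *That it distorts a comparison of short with long exposure, or of siltuximab-naive with previously treated subjects.* No EAIR by such groups is planned. The study is single-arm, has one analysis set and tests no hypothesis. Nothing says that naive subjects stop early; they differ in that their exposure clock starts only in the extension (SAP 2.4).
- *That an error of 16% or more applies to the trial's rates.* Most subjects enter on active siltuximab (Protocol 3.1), those who left a parent study for toxicity, an adverse event or progression are excluded (Protocol 4.3), and exposure is counted from the parent study.

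**Conclusion.** The mismatch holds on the text. Post-dose time enters the patient-months at risk only for subjects who had the event, so the EAIR is biased upwards whenever events occur in the window and event-free subjects have time in it.

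For the pooled safety population the size is about 1% to 3%: 1.6% to 2.7% in the rare-event, full-window case with assumed mean treatment of 60 to 36 months, and less for common events. Errors of about 8% and 16% need mean treatment of only 12 and 6 months. They would matter only if rates were reported for such subsets, which the plan does not do. All sizes rest on an assumed constant rate and assumed durations, and on reading treatment duration as SAP 4.3 defines it.

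The severity is minor: a definition to correct, with no threat to the overall safety conclusion. The limb that admits drug-related events whatever their start date is a second mismatch of the same kind, since it adds events with no corresponding event-free time.

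**What to change.** In SAP 6.1.1:

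1. Define time at risk for subjects without the event as running from the first siltuximab dose to the end of the TEAE window. The end is the earliest of last dose plus 30 days, the day before subsequent anticancer therapy, death, study withdrawal or loss to follow-up, and the data cutoff.
2. Count in the EAIR numerator only events with onset inside that same window. Report separately any drug-related events that are TEAEs only because their start date is disregarded.

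An acceptable alternative is to keep the denominator as written and restrict EAIR events to onsets on or before the last dose. Either way, the SAP should state which rule applies, and the data presentation specification should match it.

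The cost is a sentence or two of SAP text and one changed derivation. No new data are needed: AEs are already collected for 30 days after the last dose, and the plan already uses dosing, death, withdrawal and subsequent-therapy dates.
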